5.2 Analysis of secondary outcomes

Activities of daily living (ADLs) measured by the Nottingham Extended ADL scale

Analysis Set 1 will be used for analysis. All available data will be reported according to randomised treatment allocation.

The NEADL score and change from baseline at each follow-up visit will be summarised descriptively by randomised treatment group. The number with data, mean, standard deviation, median and range will be reported, see Example Table 7.

Example Table 7: NEADL

NEADL score	V	/alue at follow-up v	isit	Change from baseline			
NEADL SCOLE	Control	Fludrocortisone	Midodrine	Control	Fludrocortisone	Midodrine	
Month 3							
N							
Mean (SD)							
Median (Range)							
Month 6							
Ν							
Mean (SD)							
Median (Range)							
Month 12							
N							
Mean (SD)							
Median (Range)							

Falls and syncope (number of falls, number of fallers/non-fallers, fall rate per person year, time to first fall, fall-related injuries, number of syncopal events)

Analysis Set 1 will be used for analysis. Data from all participants with at least one falls diary available will be reported according to their randomised treatment allocation.

The number of falls reported per participant will be tabulated as frequency and percentage and summarised as mean, SD, median and range. The total number of falls and total follow-up time from participants allocated to each randomised group will be reported. The simple, unadjusted incidence rate (IR) of falls per person year (i.e. total number of falls / total follow-up time) will be calculated in each randomised treatment group and presented with 95% CIs.

The same approach as above will be used for reporting of syncopal events, and a combined outcome of falls and syncopal events.

The number of fallers (i.e. the number of participants reporting at least one fall over the 12 month period) will be reported as frequency and percentage out of those returning at least one fall diary.

Time to first fall will be calculated and tabulated by whether this was within the first 3 months from randomisation, between 3 and 6 month follow-up or after 6 month follow-up.

Fall-related injuries will be tabulated by type, with the number of participants affected and the total number of occurrences reported by randomised treatment group. The number and proportion of participants reporting at least one fall-related injury will be tabulated by treatment group. The total number of fall-related injuries reported per participant will be tabulated as frequency and percentage and as mean, SD, median and range. The total number of fall-related injuries reported in participants allocated to each treatment group will be presented. For the purpose of calculating percentages the number of participants returning at least one fall diary will be used as the denominator.

Example Table 8: Falls and syncopal events

	Control	Fludrocortisone	Midodrine
	N =	N =	N =
Number of falls			
0			
1			
>2			
Mean (SD)			
Median (Range)			
Fall rate			
Total number of falls			
Total follow-up time (years)			
Incidence rate (95% CI)			
Fallers / non-fallers			
≥1 fall / N (%)			
Time to first fall			
< 3months			
3-6 months			
>6 months			
Number of syncopal events			
0			
1			
>2			
Mean (SD)			
Median (Range)			
Syncopal event rate			
Total number of syncopal events			
Incidence rate (95% CI)			
Number of falls and syncopal events			
0			
1			
>2			
Mean (SD)			
Median (Range)			
Falls and syncope event rate			
Total number of events			
Incidence rate (95% CI)			

Standing blood pressure and postural blood pressure drop

The methods described below will be applied to the following variables; nadir standing systolic blood pressure (BP), nadir standing diastolic BP, systolic postural BP drop, diastolic postural BP drop.

Analysis Set 1 will be used for analysis. All data available will be reported according to randomised treatment allocation.

Each BP measurement and change from baseline will be summarised descriptively by randomised treatment group. The number with data, mean, standard deviation, median and range will be summarised at each visit.

Example Table 9: Blood pressure

Diago processo	V	/alue at follow-up vi	isit	Change from baseline			
Blood pressure	Control	Fludrocortisone	Midodrine	Control	Fludrocortisone	Midodrine	
Nadir standing							
Month 3*							
N							
Systolic							
Mean (SD)							
Median (Range)							
Diastolic							
Mean (SD)							
Median (Range)							
Postural drop							
Month 3*							
N							
Systolic							
Mean (SD)							
Median (Range)							
Diastolic							
Mean (SD)							
Median (Range)							

*Data will be presented in the same way for Month 6 and Month 12

Hospital admissions

Hospital admissions will be reported similarly to falls.

Analysis Set 1 will be used for analysis. Data from all participants with at least one review of hospital admissions available will be reported according to randomised treatment allocation.

The number of admissions reported per participant will be tabulated as frequency and percentage and summarised as mean, SD, median and range. Reasons for admission will also be tabulated as frequency and percentage. The total number of admissions and total follow-up time from participants allocated to each randomised group will be reported. The simple, unadjusted incidence rate of admissions per person year (i.e. total number of admissions / total follow-up time) will be calculated in each randomised treatment group and presented with 95% Cls.

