5.5 Schedule of Events

	Routine Clinical assessment	Consent contact	Clinical review	Clinical review	Clinical review	Clinical review
			Baseline Week 0	Three months	Six months Primary Endpoint	12 months
Follow-up Window	Consent, baseline and randomisation can take place at one visit if the patient receives the PIL in advance			+/- 4 weeks	+/- 6 weeks	+/- 8 weeks
Eligibility Screening	x		x			
Confirm provisional eligibility	x		x			
First approach (treating clinician)	x					
Provide PIL (RN or clinician)	x					
Written informed consent ^a	x	x				
Baseline data collection						
Demographics (DoB, gender, ethnicity) and medical history (including disease duration if PD/MSA/DLB)			x			
MDS-UPDRS parts 1, 2 and 4 (PD / MSA/DLB patients only)			x			
Height and weight			x			
Outcome measures						
Supine and standing BP ^b	x		x	x	x	x
OHQ ^c	x		x	x	x	x
EQ-5D-5L			x	x	x	x
Nottingham Extended ADLs			x	x	x	x
Health and Social Service Use Questionnaire(s)			x	x	x	x
Time and Travel Questionnaire					x	
Randomisation						
Confirm eligibility for randomisation			x			
Randomisation via Sealed Envelope			x			
Routine non pharmacological management – may vary at different sites but might include;						
Lifestyle advice may include: 
 • trigger avoidance • slow, staged, safe standing • salt intake • hydration • bolus water drinking • caffeine intake • education of condition 	x		x	x	x	x
Provide compression garments (if usual clinical practice)	x		x	x	x	x

Physical counter-manoevres (if usual clinical practice)	X		X	X	X	X
Abdominal compression (if usual clinical practice)	X		X	X	X	X
Culprit medication review	X		X	X	X	X
Participants randomised to IMP						
Pregnancy test ^d			X			
Instruction regarding IMP and local prescription arrangements ^e			X	X	X	X
Drug safety monitoring urea & electrolytes as per local practice (drug arms only) ^f			X	X	X	X
Liver function tests (midodrine arm only) as per local practice ^f			X	X	X	X
Confirmation that participant is taking IMP				X	X	X
Additional outcome measures – for all participants						
Provide participant with falls diary			X	X	X	
Falls diary review				X	X	X
Adverse Events review (including hospital admissions)				X	X	X

^a Consent should be obtained at a face-to-face clinic. If this is not possible it can be obtained via videoconference or telephone. Consent only needs to be obtained once (at routine clinical assessment or the consent contact)

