5.7 Withdrawal from the Study

Participants who withdraw once they have been randomised will not be replaced. Any reason for withdrawal will be recorded in the CRF and participant's medical notes.

Where participants state they want to withdraw from the study, sites should try to ascertain the reason for withdrawal and document this within the CRF and participant's medical notes.

If a participant does not want to attend any further study follow-up consultations but is willing to carry out questionnaires over the phone or by post they may continue in the study. This is not a withdrawal of consent and routinely collected data such as clinical postural BP can be collected from the medical records and documented in the CRF.

Where a participant decides to withdraw their consent and does not wish to participate in any further research activity they will be asked to choose from the following withdrawal options:

1. Withdraw from further research activity but allow the use of data collected up to the point of withdrawal and any future routinely collected data from medical records where relevant to the outcomes of the study.
2. Withdraw from further research activity and allow the use of data collected up to the point of withdrawal but does not allow the use of any routinely collected data from the point of withdrawal.

In all cases, data collected up to the point of withdrawal will be retained and included in the analysis unless the participant specifically requests the removal of this data. Unless a participant declines the collection of routine data from medical records after they have withdrawn from the study, at 12 months sites will obtain data on blood pressure recordings, hospital admissions, procedures/operations and outpatient visits that have occurred in the duration of the study.

If the participant loses capacity they will be withdrawn from the study. However, if the investigator judges the loss of capacity to be reversible and short-term (e.g. acute delirium) and appropriate, the participant will continue in the study. This situation will be assessed on a case-by-case basis.

The occurrence of an Adverse Event is not a reason to withdraw a patient from the study.

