7.2 Recording Adverse Events and Adverse Reactions (AEs and ARs)

All AEs and ARs will be recorded from the date of randomisation until completion of 12-month visit or until the participant withdraws. Participants will be asked about AEs and ARs at each scheduled study visit.

All AEs and ARs (unless listed below in 7.3) will be recorded in the participants' medical notes and the data entered onto the AE page in the electronic case report form (eCRF). The local site PI's clinical judgement should be used to determine if an AE is reportable as an AR.

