Participants will be classed as fallers if they report at least one fall over the 12 month period and a non-faller if they did not report a fall and returned at least one fall diary; i.e. participants who do not return at least one fall diary will be excluded from the analysis. We will also categorise participants as a single faller if they fall once, a recurrent faller if they fall twice or more, and a non-faller if they do not report any falls.

The number of faints (syncopal events) for each participant will be summed over the 12 month period. The syncopal event rate will be calculated as described above. In addition, we will report the total number, and rate of, a combined outcome of fall and faints.

Time to first fall will be measured as the time from randomisation to the first reported fall.

Fall related injuries are reported as free-text fields. There will be a medical review of any coding of free-text fields required.

Standing blood pressure and postural blood pressure drop

The lowest (nadir) standing blood pressure (systolic and diastolic) is measured at baseline, three, six and 12 month follow-up.

Blood pressure will also be measured in the supine position (lying down) at baseline, three, six and 12 month follow-up.

Postural blood pressure drop will be defined as (supine – lowest standing blood pressure) for systolic and diastolic measurements at each time point.

For each measurement the change from baseline will also be calculated as the follow-up value minus the baseline value.

Hospital admissions

Hospital admissions during the 12 month trial period will be collected from medical records. The number of admissions per participant will be calculated.

Reasons for admission will be tabulated. 'Other' reasons will be coded/grouped where possible with a medical review of any coding.

The rate of hospital admissions per person year will be calculated in each arm as the total number of admissions from all participants in that arm divided by the total observation time for all participants in that arm. For each participant their observation time will be measured as the time (in years) from randomisation to their last completed follow-up visit.

Side effects and the safety data associated with each treatment strategy

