2.5 Study assessments

Participants are assessed at three, six and 12 months from trial entry. As this is a pragmatic trial, assessments can take place within +/- 4, 6 and 8 weeks for the three, six and 12 month visits respectively. A simplified schedule of assessment is given in **Table 1**.

		Visit			
Form		Month 3	Month 6	Month 12	
	Baseline	(+/- 4 weeks)	(+/- 6 weeks)	(+/- 8 weeks)	
Demographics	Х				
Medical History	Х				
UPDRS*	Х				
Blood pressure	Х	Х	Х	Х	
Culprit medication review	Х	Х	Х	Х	
ОНQ	Х	Х	Х	Х	
NEADL	Х	Х	Х	х	
EQ-5D-5L	Х	Х	Х	Х	
Falls diary return		Х	Х	Х	
Hospital admission review		Х	Х	Х	

Table 1: Simplified schedule of assessments

*Only for participants with Parkinson's disease, Dementia with Lewy bodies or Multi System Atrophy

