3.4 Analysis sets

The following analysis sets will be defined:

Analysis Set 1	 Participants will be analysed according to the treatment group they were randomised to receive, i.e. following the intention-to-treat (ITT) principle All available outcome data will be included in the analysis
Analysis Set 2	 Participants will be analysed according to the treatment group they were randomised to receive, i.e. following the intention-to-treat (ITT) principle Outcome data following cross-over to an alternative treatment group, or discontinuation of allocated trial treatment, will be set to missing
Safety Analysis Set (SAS)	 For each treatment group, the Safety Analysis Set will comprise all participants exposed to that treatment strategy Safety data (adverse events) will be summarised according to the treatment strategy received at the time of onset of each adverse event. Participants who cross-over between treatment groups will be included in the Safety Analysis Set for each treatment group

Primary and secondary clinical outcome measures will be reported according to randomised treatment group; safety data will be reported according to the treatment strategies received. Analysis Set 1 will be the main analysis set used to report the primary and secondary clinical outcome measures. Analysis Set 2 may also be used to provide supplementary information on the primary outcome measure. All safety data will be reported using the Safety Analysis Set.

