Appendix Table 4: Blood pressure

Hospital admissions

Hospital admissions would be analysed similarly to falls.

Analysis Set 1 would be used for analysis. All participants with at least one review of hospital admissions available would be analysed according to their randomised treatment allocation.

The number of admissions reported per participant would be tabulated as frequency and percentage and summarised as mean, SD, median, IQR and range. Reasons for admission would also be tabulated as frequency and percentage. The number, or percentage, of admissions may also have been presented graphically. The total number of admissions and total follow-up time from participants allocated to each randomised group would be reported. The simple, unadjusted incidence rate of admissions per person year (i.e. total number of admissions / total follow-up time) would be calculated in each randomised treatment group and presented with 95% Cls.

A mixed-effects negative binomial regression model would be fitted to the admissions data. Site would be included as a random effect and treatment assignment, baseline age (<80 years or >=80) and aetiology (neurogenic or non-neurogenic) as fixed effects. The log of the exposure variable (follow-up time) would be included in the model with the coefficient constrained to be one.

From this model we would obtain the estimated incidence rate ratio and risk difference in the admission rate per person-year between fludrocortisone and control and midodrine and control. These estimates would be reported with corresponding 95% confidence intervals.

As for falls data, a Poisson or zero-inflated model may have been used if this was more suitable for the distribution of the data.

c. Additional / Exploratory analyses

A pre-specified exploratory analysis would compare the clinical effectiveness of fludrocortisone with midodrine for the primary outcome. This would use the same model as for the primary analysis but with fludrocortisone as the reference group.

d. Missing data

i. Intention-to-treat / treatment policy estimand

The availability of outcome data would be summarised as described in section 4.1.3.

The characteristics of participants with and without a six month OHQ score would be explored. Characteristics to be summarised would have included baseline OHQ score, age, aetiology, gender, three month OHQ score (where available) and postural blood pressure drop (where available).

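### The hospital-admissions summary depends on an undefined admissions review, first scheduled at month 3, and on person-time that stops at the latest completed visit, so early deaths and losses can drop out with admissions already known

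*SAP*

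**What the plan says.** - **Entry rule.** SAP section 5.2, under hospital admissions, names Analysis Set 1 and then adds: "Data from all participants with at least one review of hospital admissions available will be reported according to randomised treatment allocation". The SAP Appendix repeats the rule for the full-enrolment analysis: "All participants with at least one review of hospital admissions available would be analysed according to their randomised treatment allocation".
- **Analysis Set 1.** SAP section 3.4 defines it by randomised arm and states: "All available outcome data will be included in the analysis".
- **Timing.** SAP section 2.5, Table 1, marks the "Hospital admission review" at months 3, 6 and 12, with none at baseline. The protocol's Schedule of Events (section 5.5) agrees and places it within the adverse event review.
- **Source.** SAP section 2.4.2: "Hospital admissions during the 12 month trial period will be collected from medical records".
- **Person-time.** The same section runs each participant's observation time from randomisation to the latest follow-up visit that was completed.
- **After withdrawal.** Protocol section 5.7 provides that, unless the participant declines, "at 12 months sites will obtain data on blood pressure recordings, hospital admissions, procedures/operations and outpatient visits" covering the duration of the study. SAP section 4.1.3 also allows routine data from records after withdrawal.
- **Safety route.** Protocol section 7.2: "All AEs and ARs will be recorded from the date of randomisation". Inpatient hospitalisation is a seriousness criterion (section 7.1), and serious events exempt from immediate reporting still go on the adverse event log (section 7.7).

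**The concern.** The rule resembles the one for falls, where a participant needs at least one returned diary. That suits falls, because without a diary there are no data. Admissions have sources that do not depend on the participant returning anything.

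Having a review is a post-randomisation condition, and it can be related to the outcome: someone admitted early and seriously ill is more likely than others to die or be lost before the first review. Leaving such people out lowers the arm's admission rate and its proportion admitted, most in the arm with most early harm. The protocol's rationale (section 1.2) raises the possibility of more hospitalisation with fludrocortisone than with midodrine, so the admissions table will be read with that question in mind.

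The person-time rule adds a second difficulty. It is tied to visits while the events are tied to records, so the numerator and denominator of the rate can cover different periods.

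**Working it through.** **Step 1: apply the rules to each type of participant.**

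| Participant | Possible source of admissions | Is there a review? | Person-time under SAP 2.4.2 |
|---|---|---|---|
| Dies before the month-3 visit | Medical records, adverse event log | None due yet; no rule for a records check after death | No completed visit, so undefined |
| Lost before month 3, not formally withdrawn | Medical records, adverse event log | Not stated that records will be checked | Undefined |
| Withdraws before month 3, allows routine data | 12-month records extraction | Not stated whether the extraction is a review | Undefined |
| Withdraws before month 3, declines routine data | Data collected before withdrawal, which protocol 5.7 keeps unless removal is requested | None | Undefined |
| Withdraws after month 3, allows routine data | Month-3 review plus 12-month extraction | Yes | Stops at the latest visit, although admissions are retrieved to 12 months |

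Rows 1, 2 and 4 can lose known admissions. Row 3 depends on how the analyst reads the word review. Rows 3 and 5 have admissions without matching time.

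**Step 2: length of the unseen period.** Month 3 is week 13, and the window adds 4 weeks: 13 + 4 = 17 weeks, or 17/52 = 0.33 years.

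**Step 3: size of the omission.** The plan states no admission rate, so there is no figure of its own to reproduce. Inputs:

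- n = 122 per arm, the planned size (SAP 2.6). The trial closed early, so this is not the achieved size.
- Assumed: k = 2 to 9 lost before month 3 without a review, each with 0.125 years of follow-up.
- Assumed: a share a = 0.5 to 1.0 of them admitted once.
- Assumed: r = 0.3 to 0.6 admissions per person-year in the rest, each followed for one year.

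With the early losses left out, the rate is r. With everyone in, it is [r(n − k) + ka] / [(n − k) + 0.125k].

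- Smallest effect (k = 2, a = 0.5, r = 0.6): (72 + 1)/(120 + 0.25) = 0.607 against 0.600, an understatement of 1.2%.
- Largest effect (k = 9, a = 1.0, r = 0.3): (33.9 + 9)/(113 + 1.125) = 0.376 against 0.300, an understatement of 20.2%.

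A small-arm illustration, also assumed: 20 participants, 2 lost early after one admission each with 0.12 years apiece, and 18 others with 9 admissions in 18 person-years, 7 of them admitted at least once. Without the two: 9/18 = 0.50 per person-year and 7/18 = 39% admitted. With them: 11/18.24 = 0.603 and 9/20 = 45%. The understatement of the rate is 1 − 0.50/0.603 = 17%.

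**Step 4: size of the person-time mismatch.** If the early losses in the largest case are counted with no time, the rate is 42.9/113 = 0.380 against 0.376, a trivial difference because their follow-up was short. It is larger for withdrawers with records to 12 months. Suppose the same 9 are early withdrawers with one admission each over a full year of record coverage. Matching time is 113 + 9 = 122 years, giving 42.9/122 = 0.352. Counting their admissions with no time gives 0.380, which is 0.380/0.352 − 1 = 8% too high. This error runs in the opposite direction to the omission in step 3.

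**The case against.** The strongest reply is that a review need not mean an attended visit. Protocol section 10.2 lists medical notes as a source for admissions, so a site can complete a review for someone who never came back, including at months 6 or 12 for a participant who was lost. Analysis Set 1 promises all available data, and most early withdrawers have a records extraction by default. On that reading few people are excluded.

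Much of this stands. A reader might infer that everyone who leaves before month 3 is dropped, or that exclusion is certain for deaths. The documents do not support either inference: routine data are retrieved after withdrawal unless declined, and nothing prevents a records check after a death. Nor do they show that any arm's rate is 17% or 20% too low, or that a comparison involving fludrocortisone is biased. The protocol's remark on hospitalisation is tentative and says nothing about the first three months.

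The consequences are also limited. SAP section 3.3 rules out statistical testing, section 5.2 plans only simple rates by arm for this outcome, and early hospitalisations meeting the serious-event definition appear in the safety summaries of section 6.2. Those summaries group events by treatment at onset rather than by randomised arm, so some disagreement with the admissions table is expected anyway.

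What the reply does not settle is the wording. The SAP neither defines a review nor says that the 12-month extraction is one. It gives no admissions rule for a death before month 3, and it defines no person-time for someone with no completed visit.

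**Conclusion.** The point holds in limited form. The entry rule allows early deaths, early losses and those who decline record use before any review to be excluded with admissions the trial already knows about. Whether early withdrawers with extracted records are included is left to interpretation and, if they are, the rate has no matching time for them.

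The size cannot be established, because the documents give no admission rate, early-loss rate or achieved number per arm. The 1% to 20% understatement describes only the assumed ranges, and the 8% overstatement from unmatched time is likewise an illustration. The outcome is secondary and reported descriptively, so this is a low-priority improvement. It is still worth making, because with few participants one or two exclusions can visibly move a rate.

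**What to change.** Replace the entry and person-time rules in SAP sections 2.4.2 and 5.2, and mirror the change in the Appendix:

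1. Include all randomised participants with any admissions source: a visit review, the 12-month records extraction, or a check of records and the adverse event log for deaths and losses.
2. For those who decline later record use, keep admissions already recorded before withdrawal, unless they asked for their data to be removed.
3. End both the counting of admissions and person-time at the earliest of 12 months, death, or the end of permitted or available record coverage.
4. Report per arm the number of participants with no admissions source.

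The cost is SAP wording and a check of existing records and the adverse event log for the few participants without a month-3 review. No new participant contact is needed.
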